11.4 Power and Sample Size

Per analysis of our retrospective human data and preclinical data, we estimate that the mean cortical thickness for both cases and controls pre SBRT will be approximately 1.35 mm. At 3 months, in the absence of any treatment, we estimate approximately 16.7% loss of cortical thickness to bones to 1.13 mm (thus resulting in a mean change of 0.22 mm in controls) within the treatment field in regions of bone receiving ≥ 30 Gy. Conservatively, if risedronate use limits loss of cortical thickness by at least half on a percentage scale (i.e., expected cortical thickness at 3 months in treatment group 8.4% lower, or 1.24 mm, corresponding to an expected mean change in treatment group of 0.11 mm), and assuming a standard deviation of delta cortical thickness in both treatment and control patients of 0.20,⁴ then with a power of 0.80 and a one-tailed alpha of 0.05, we anticipate that we will need 42 patients per group to achieve desired power to illustrate significantly higher preservation of cortical thickness at 3 months post SBRT.

There is no human data to accurately estimate how significantly risedronate will limit bone loss following SBRT, however in our pre-clinical rodent models, cortical thickness was preserved in all mice receiving risedronate and in two mice cortical thickness increased. We have no mechanistic reason to suspect that risedronate would cause increased bone loss and therefore are utilizing a one-tailed alpha in our calculations.

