3.1 Inclusion Criteria

- 3.1.1 Patients must be 18 years or older, but there is no upper limit on age of inclusion.
- 3.1.2 Patients must have a peripheral lung tumor that is amenable to SBRT as determined by the treating radiation oncologist. To be classified as a peripheral lung tumor, the tumor edge (the edge of the gross tumor volume or GTV in radiation treatment planning software) must be within 2 cm of the chest wall. This is determined by the treating radiation oncologist. The chest wall is defined as the chest wall musculature or ribs/vertebrae immediately adjacent to the lungs.
- 3.1.3 Patients must have ECOG status of 0-3
- 3.1.4 Patients must have a life expectancy of at least 3 months as determined by the treating radiation oncologist.
- 3.1.5 Patients must have the ability to understand and the willingness to sign an IRB-approved informed consent document.

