3.3 Inclusion of Women and Minorities

Men and women of all races and ethnicities who meet the above-described eligibility criteria are eligible to participate in this study. The study consent form will also be provided in Spanish for Spanish-speaking participants.

Based on WFBCCC population estimates, we may expect approximately 44% of participants to be women. Translating this to our sample size estimate of 84 patients, we may enroll approximately 42 women. We may enroll approximately 10-13% Black or African American patients. Based on our catchment area and hospital demographics we do not expect high accruals of individuals of Hispanic/ Latino, American Indian/Alaska Native or Asian ancestry; however, no individual will be excluded from the study if they satisfy the above inclusion/exclusion criteria. Should we not meet or exceed these estimates, the PI will engage the Office of Cancer Health Equity to discuss strategies to enhance recruitment in these target populations.

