5.0 Study Outcomes and Study Measures

All CT imaging referenced below is performed as a routine standard of care and necessary for cancer treatment follow-up. These chest CT scans utilized in this research protocol would be performed every 3 months regardless of inclusion on this trial.

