6.4 Duration of Follow-up

Follow-up for serious adverse events and mortality after the single dose of 150 mg of risedronate or placebo is administered will take place during the routine clinic visits during radiation treatment. Radiation treatments will occur within 1 – 3 weeks of taking the study drug. The 30 day follow-up window that is part of mandatory DSMC-SAE reporting will be considered 30 days from the end of all treatments of radiation. This visit can be either a phone call or a visit in person to review adverse events and may be conducted and documented in the medical record by either research study staff RNs or the treating physician. A window of +/- 7 business days is allowed for the 30 day followup assessment.

Specific toxicity related to radiation pneumonitis, radiation fibrosis, and chest wall pain will be collected at each followup point as per appendices K – M.

Patients removed from study for unacceptable adverse events will be followed until resolution or stabilization of the adverse event.

Patients will be followed for a minimum of 3 months for assessment of the primary objective.

Patients will be ideally followed in total for 12 months after completion of radiation therapy for the purposes of this study.

In the event that patients develop progressive disease or a new cancer, requiring additional chemotherapy they will be withdrawn from further study directed followup. In these situations, the followup schedules and imaging become dramatically different from what is directed on this protocol. Additionally further systemic chemotherapy treatments can heavily alter bone density/cortical thickness. As such, if patients develop new disease requiring additional systemic chemotherapy treatment outside of their initial SBRT, they will be withdrawn from study for further follow ups/study directed imaging. Any data that was collected prior to study withdrawal will still be used in analysis. **Immunotherapy or**

hormonal therapy for breast or prostate cancer will not be considered reasons for withdrawal.
Cryoablation or radiofrequency ablation will not be considered a reason for withdrawal from study.

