11.0 Statistical Considerations

11.1 Analysis of Primary Objective

The percent change in mean cortical thickness within regions receiving 30 Gy or more will be calculated from time of the treatment planning CT scan to 3 months post SBRT. This % change will be compared between the patients receiving risedronate and those receiving placebo.

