11.5 Estimated Accrual Rate

On review of treatment planning records for the last 1 month in our department here at the main campus of Wake Forest Hospital, we have treated 18 patients who would have qualified for inclusion on this study. This is a reasonable representation of our average treatment population. Conservatively, we estimate accrual of 5 – 10 patients per month. Roughly 2/3 of our SBRT plans unavoidably exceed dosimetric constraints for the ribs/chest wall.

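### Section 11.4's 42 per group is the evaluable number for 0.80 power, with no allowance for patients lacking a 3-month value in bone at 30 Gy or more

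*Combined protocol and SAP*

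**What the plan says.** Section 11.4 assumes a mean 3-month loss of 0.22 mm in controls and 0.11 mm on risedronate, SD of change 0.20, power 0.80 and one-tailed alpha 0.05, and concludes that "we anticipate that we will need 42 patients per group to achieve desired power". Section 3.3 repeats the figure as the trial's size: "Translating this to our sample size estimate of 84 patients". Neither section says whether 84 is the number randomised or the number with a primary value. No dropout rate, inflation factor, replacement rule or method for a missing 3-month value appears.

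The primary measure exists only for some bone and at one visit: the percent change "within regions receiving 30 Gy or more will be calculated from time of the treatment planning CT scan to 3 months post SBRT" (section 11.1). Four other provisions bear on who will have it.

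- Eligibility is by distance. Under 3.1.2 the tumor edge "must be within 2 cm of the chest wall"; no bone dose is required.
- Life expectancy need only be 3 months (3.1.4).
- Section 6.4 says that "if patients develop new disease requiring additional systemic chemotherapy treatment outside of their initial SBRT, they will be withdrawn from study" for further follow-up and study imaging, and also that "Any data that was collected prior to study withdrawal will still be used in analysis".
- The CTs are routine and "would be performed every 3 months regardless of inclusion on this trial" (section 5.0). Footnote f of the study calendar (6.6) gives each a window of +/- 8 weeks.

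For the 3- to 12-month course of cortical thickness, section 11.2.1 names repeated measures ANOVA with no rule for missing visits.

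**The concern.** A sample size computed with no margin delivers its stated power only if nearly every randomised patient yields the primary value. The protocol describes three ways in which one may not.

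- **Death.** The minimum life expectancy is 3 months, but the primary CT is 3 months after SBRT. Dosing precedes SBRT by 7-21 days, and SBRT generally takes 1.5-2 weeks (6.1, 6.3). Counted from dosing to a CT 3 months after SBRT ends, that is nominally 3 months plus 2.5 to 5 weeks.
- **Withdrawal.** Metastatic tumors are eligible (section 3.0), and new systemic chemotherapy ends study imaging. Keeping earlier data does not supply a 3-month value for someone who left before that CT.
- **Dose.** A tumor within 2 cm of the chest wall may leave no bone at 30 Gy or more, and no rule covers such a patient.

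Two things are at stake: the accuracy of the stated 0.80, and the absence of any rule, fixed before unblinding, on who belongs in the primary comparison. A related gap affects the secondary analysis. Classical repeated measures ANOVA omits any patient with a missing visit, which does not fit section 6.4's commitment to use data collected before withdrawal.

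**Working it through.** **Inputs (section 11.4).** Baseline 1.35 mm; loss 16.7% in controls and 8.4% on risedronate; SD of change 0.20 (read as mm) in both arms; one-sided alpha 0.05; power 0.80; equal arms.

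**Step 1. Difference between arms.**
- Rounded, as printed: 0.22 - 0.11 = 0.11 mm; standardized, 0.11 / 0.20 = 0.55.
- Unrounded: 1.35 x (0.167 - 0.084) = 0.11205 mm; standardized, 0.56025.

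**Step 2. Reproduce the plan's figure.**
- Normal approximation, rounded difference: n per group = 2 x [0.20 x (1.645 + 0.842) / 0.11]^2 = 40.9, so 41.
- Two-sample t-test: power = P(T > critical t), with T noncentral t on n1 + n2 - 2 degrees of freedom and noncentrality difference / [SD x sqrt(1/n1 + 1/n2)]. At 42 + 42, noncentrality is 0.55 x sqrt(21) = 2.520, critical t on 82 df is 1.664, and power is 0.804. At 41 + 41 it is 0.795. The smallest equal group size reaching 0.80 is therefore 42, the plan's number.
- A two-sided test would need 53 per group, so 42 is the one-sided t-test size and contains no inflation.

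**Step 3. Margin before power drops below 0.80.**

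| Evaluable | Power, 0.11 mm | Power, 0.11205 mm |
|---|---|---|
| 42 + 42 | 0.804 | 0.816 |
| 41 + 42 | 0.799 | 0.812 |
| 41 + 41 | 0.795 | 0.808 |
| 40 + 41 | 0.791 | 0.804 |
| 40 + 40 | 0.786 | 0.799 |

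The margin of three patients in the right-hand column comes from rounding and is not a planned allowance.

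**Step 4. Power if 84 are randomised and some lack the value.** The loss rates are assumptions; the documents give none. Evaluable n per arm = 42 x (1 - loss).

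| Assumed loss | n per arm | Power, 0.11 mm | Power, 0.11205 mm |
|---|---|---|---|
| 5% | 39.9 | 0.785 | 0.798 |
| 10% | 37.8 | 0.766 | 0.779 |
| 15% | 35.7 | 0.744 | 0.758 |
| 20% | 33.6 | 0.721 | 0.735 |

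**Step 5. Enrolment if 84 is meant as evaluable.** 42 / (1 - loss), rounded up: 45 per group (90) at 5%, 47 (94) at 10%, 53 (106) at 20%.

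**Step 6. Section 11.2.1 under complete-case ANOVA.** Four follow-up visits, with 5% or 10% of scans missing at each (assumption).
- Missing independently: 84 x 0.95^4 = 68.4; 84 x 0.90^4 = 55.1.
- The same patients missing every time: 84 x 0.95 = 79.8; 84 x 0.90 = 75.6.

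Complete cases would number about 68 to 80 of 84 at 5%, and 55 to 76 at 10%.

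**Limit.** Section 11.4 powers the change in mm while the endpoint is percent change, so these figures carry over only as far as that substitution holds.

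**The case against.** The strongest reply is that the demonstrable shortfall is slight. With no loss rate in the documents, every figure in step 4 is conditional. The primary CT is routine, comes early and has a 16-week window in all, so few values should be lost to late scans. At 5% loss with the unrounded difference, power is 0.798. This stands as to size. It does not remove the other routes: the window does not help with death, withdrawal before the scan, or absence of bone at 30 Gy or more.

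Second, other assumptions matter as much. An SD of 0.21 with no loss gives 0.769 (0.11 mm), about the same as 10% attrition. Section 11.4 calls its effect conservative; if risedronate prevented 55% of the loss, 20% attrition would still leave 0.791 to 0.808. This is fair, and it means the crossing at one lost patient should not be over-read. However, section 11.4 also says that no human data exist on the size of the effect, so a larger effect cannot serve as the allowance.

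Third, section 11.5 says that roughly 2/3 "of our SBRT plans unavoidably exceed dosimetric constraints for the ribs/chest wall", which suggests that most patients will have bone at 30 Gy or more. But the constraint tables in section 6.1 give no rib value, so this fraction cannot be tied to 30 Gy, and the size of the dose route is unknown in either direction.

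Fourth, section 11.2.1 does not specify the complete-case form of ANOVA. That is so; the conflict with 6.4 arises under the classical form, and the text leaves the choice open.

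A reader might also infer from section 6.5, which removes patients meeting any criterion in 3.2, that the study dose itself triggers removal under 3.2.3 and so depletes one arm. The documents do not support that: 3.2 is an entry list, reading 3.2.3 to cover the study dose is strained, and only the pharmacy holds the allocation. It is a wording problem.

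**Conclusion.** The point holds in moderate form. The 84 patients are the bare evaluable number for 0.80 power under section 11.4's own inputs; the text makes no allowance for a missing primary value, yet contains three routes to one. Against the 0.80 target, the cost is 0.2 to 1.5 points at an assumed 5% loss, 2.1 to 3.4 at 10%, and 6.5 to 7.9 at 20%.

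A reader might infer that the trial is materially underpowered. The documents do not show that: the larger shortfall needs about 20% loss by the 3-month CT, and nothing in them points to that rate. What they do show is that 0.80 is unqualified where it should be conditional, and that the primary analysis set is undefined.

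The section 11.2.1 point stands separately: 6.4 withdraws some patients over 12 months but promises to use their earlier data, and a method that may discard incomplete patients does not fit. The mismatch among 6.5, 3.2, 6.3 and 6.4 is minor.

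**What to change.** 1. **Section 11.4.** State whether 84 is randomised or evaluable. If randomised, state the assumed evaluable fraction and give the power for it from step 4. If evaluable, state the enrolment needed (step 5). Define the primary set as randomised patients whose plan, made blind to arm, contains bone at 30 Gy or more and who have a 3-month CT. Report exclusions from it by arm, with reasons.
2. **Section 11.2.1.** Replace repeated measures ANOVA with a mixed model for repeated measures (arm, visit, arm x visit, baseline thickness) on all available scans. Fit the same model to the 30 Gy-or-more region as a sensitivity analysis of the primary result, so that a patient who missed only the 3-month CT still contributes.
3. **Section 6.5 (minor).** Reconcile it with 3.2, 6.3 and 6.4. Section 3.2 lists entry exclusions, and 6.5 does not cite the criteria listed in 6.3.

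**Cost.** If 84 is the number randomised, this is protocol and SAP wording only, with no added patients, visits or scans, and a slightly lower stated power. If 84 is meant as evaluable, more patients are needed. Even 106 at section 11.5's lower rate of 5 per month takes about 21 months (106 / 5 = 21.2), plus 12 months of follow-up: about 33 months, within the 2-3 years in section 11.6.

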11.5 Estimated Accrual Rate

On review of treatment planning records for the last 1 month in our department here at the main campus of Wake Forest Hospital, we have treated 18 patients who would have qualified for inclusion on this study. This is a reasonable representation of our average treatment population. Conservatively, we estimate accrual of 5 – 10 patients per month. Roughly 2/3 of our SBRT plans unavoidably exceed dosimetric constraints for the ribs/chest wall.

11.6 Estimated Study Length

2 - 3 years

Appendix A – Eligibility Checklist

IRB Protocol No.	WFBCCC Protocol No. 99518
Study Title: CCCWFU # 99518	
A Randomized Clinical Trial of Prophylactic Risedronate for Patients with Peripheral Lung Tumors Treated with SBRT	

Principal Investigator: [name] MD

Inclusion Criteria (as outlined in study protocol)	Criteria is met	Criteria is NOT met	Source Used to Confirm * (Please document dates and lab results)
Patients must be 18 years or older, but there is no upper limit on age of inclusion.			
Patients must have a peripheral lung tumor that is amenable to SBRT as determined by the treating radiation oncologist. To be classified as a peripheral lung tumor, the tumor edge (the edge of the gross tumor volume or GTV in radiation treatment planning software) must be within 2 cm of the chest wall. This is determined by the treating radiation oncologist. The chest wall is defined as the chest wall musculature or ribs/vertebrae immediately adjacent to the lungs.			
Patients must have ECOG status of 0-3			
Patients must have life expectancy of at least 3 months as determined by the treating radiation oncologist			
Patients must have the ability to understand and the willingness to sign an IRB-approved informed consent document (either directly or via a legally authorized representative)			
Exclusion Criteria (as outlined in study protocol)	Criteria NOT present	Criteria is present	Source Used to Confirm * (Please document dates and lab results)
Tumor edge is greater than 2 cm from the chest wall. The edge of tumor is the edge of the gross tumor volume or GTV as defined in radiation treatment planning software. This is determined by the treating radiation oncologist			
Tumors that are expected to require more than 10 fractions of radiation as determined by the treating radiation oncologist.			
History of using bone anti-resorptive agents including bisphosphonates or RANK-L inhibitors within the last 1 year.			

Inability to stand or sit upright for at least 30 minutes, which is necessary for ingestion of risedronate.			
Hypocalcemia defined as serum total calcium lower than 8.5 mg/dL on most recent bloodwork that is within 3 months of administration of study drug/placebo			
Severe renal impairment (EGFR <30 mL/min) on most recent bloodwork that is within 3 months of administration of study drug/placebo			
Known allergy to zoledronate or other bisphosphonates			
Surgery affecting the bone or dental operations within the last 6 months Dental operations do not include routine cleaning or cavity fillings Dental operations that exclude patients refer to any manipulation of mandible *This will be explicitly asked and documented by treating radiation oncologist in the EMR			
Positive urine pregnancy test in women of child bearing potential within 1 week of registration. Pregnant women are excluded from this study because radiation has clear teratogenic and potentially abortifacient risks.			

This subject is eligible / ineligible for participation in this study.

OnCore Assigned PID: _____

Signature of research professional confirming eligibility: _____

Date: ____ / ____ / ____

Signature of Treating Physician: _____

Date: ____ / ____ / ____

Signature of Principal Investigator**: _____

Date: ____ / ____ / ____

* Examples of source documents include clinic note, pathology report, laboratory results, etc. When listing the source, specifically state which document in the medical record was used to assess eligibility. Also include the date on the document. Example: "Pathology report, 01/01/14" or "Clinic note, 01/01/14"

**Principal Investigator signature can be obtained following registration if needed

Appendix B – Protocol Registration Form

DEMOGRAPHICS

Patient: Last Name: _____ First Name: _____

MRN: _____ DOB (mm/dd/yy): ____ / ____ / ____

ZIPCODE: _____

SEX: Male Female

Ethnicity (choose one): Hispanic
 Non-Hispanic

Race (choose all that WHITE BLACK ASIAN

apply): PACIFIC ISLANDER NATIVE AMERICAN

Height: _____.____ inches Weight: _____.____ lbs.(actual)

Surface Area: _____.____ m²

Primary Diagnosis: _____

Date of Diagnosis: ____ / ____ / ____

Performance Status: ____ ECOG

PROTOCOL INFORMATION

Date of Registration: _____ / _____ / _____

MD Name (last) : _____

Date protocol treatment started: _____ / _____ / _____

Informed written consent: YES NO

(consent must be signed prior to registration)

Date Consent Signed: _____ / _____ / _____

PID # (to be assigned by OnCore): _____

Protocol Registrar can be contact by calling [contact] between 8:30 AM and 4:00 PM, Monday – Friday.

Complete the eligibility checklist in WISER and then give the completed Eligibility Checklist and Protocol Registration Form must be hand delivered, faxed or e-mailed to the registrar at [contact] or [contact], respectively.

Appendix C – Race & Ethnicity Verification Form

Thank you so much for helping us to verify your race and ethnicity to ensure the quality of our information. As a brief reminder, the information you provide today will be kept confidential.

1. Are you:
 Hispanic or Latino/a
 Not Hispanic or Latino/a
2. What is your race? One or more categories may be selected.
 White or Caucasian
 Black or African American
 American Indian or Alaskan Native
 Asian
 Native Hawaiian or Other Pacific Islander
 Other, Please Specify: _____

Internal use only:

Name: _____ MRN#: _____

Was the self-reported race and ethnicity of the participant verified at the time of consent?

Yes No

Was a discrepancy found? Yes No

If yes, please provide what is currently indicated in the EMR:

Ethnicity: _____ Race: _____

Additional comments: _____

Appendix D – Mandatory DSMC SAE Reporting Guidelines

Data and Safety Monitoring Committee (DSMC) Serious Adverse Event (SAE) Notification SOP	Date: 02/11/2021
---	-------------------------

Mandatory DSMC SAE Reporting Requirements in WISER

This document describes reporting requirements of adverse events from **WFBCCC Investigator Initiated interventional trials to the Data and Safety Monitoring Committee (DSMC)**. A trial is considered a **WFBCCC Investigator Initiated interventional trial** if the following criteria are met:

- 1) The Principal Investigator (PI) of the trial is a member of a department at the Wake Forest University Baptist Medical Center.
- 2) WFBCCC is considered as the primary contributor to the design, implementation and/or monitoring of the trial.
- 3) The trial is designated as “Interventional” using the Clinical Research Categories definitions provided by the NCI in the Data Table 4 documentation.
(<https://cancercenters.cancer.gov/GrantsFunding/DataGuide#dt4>)

There are two distinct types of WFBCCC Investigator Initiated interventional trials based on where patient enrollment occurs. These include:

- 1) Local WFBCCC Investigator Initiated interventional trials defined as trials where **all patients are enrolled from one of the WFBCCC sites**. These include the main outpatient Cancer Center clinics (located in Winston-Salem) as well as WFBCCC affiliate sites located in Bermuda Run (Davie Medical Center), Clemmons, Lexington, High Point, or Wilkesboro.
- 2) Multi-Center WFBCCC Investigator Initiated interventional trials defined as trials where patients are enrolled from other sites in addition to WFBCCC sites.
There are three types of trials that are included in this category:
 - a. Trials sponsored by the NCI Community Oncology Research Program (NCORP) that are conducted at multiple sites where the PI is a member of a department at the Wake Forest University Baptist Medical Center.
 - b. Trials sponsored by Industry that are conducted at multiple sites and the PI is a member of a department at the Wake Forest University Baptist Medical Center.
 - c. Trials sponsored by WFBCCC that are conducted at multiple sites and the PI is a member of a department at the Wake Forest University Baptist Medical Center.

All Adverse Events (AEs) and Serious Adverse Events (SAEs) that occur on any patients

enrolled on WFBCCC Investigator Initiated Interventional trials must be entered into the WISER system. The only exception to this requirement is for patients enrolled on NCORP trials at non- WFBCCC sites. AEs and SAEs for NCORP patients enrolled at WFBCCC sites must be entered into the WISER system. Once these AEs and SAEs are entered in WISER, certain actions must be taken regarding the reporting of specific Adverse Events to the DSMC.

All Adverse Events that occur during protocol intervention (defined below) and are coded as either 1) **unexpected grade 4**, 2) **unplanned inpatient hospitalization \geq 24 hours (regardless of grade)**, or **grade 5 (death)** must be reported to the DSMC using the SAE console in WISER.

A research nurse or clinical research coordinator when made aware that an adverse event meets one of the above criteria has occurred on a WFBCCC Investigator Initiated interventional trial, is responsible for informing a clinical member of the DSMC by phone (or in-person) about the adverse event. The nurse/coordinator should contact the treating physician prior to calling the DSMC clinical member to obtain all details of the SAE, as well as all associated toxicities to be recorded along with the SAE. In addition, this nurse or coordinator is responsible for entering the adverse event information into the SAE console in WISER. Once the adverse event has been entered into the SAE console an email informing the entire DSMC will be generated.

THESE REPORTING REQUIREMENTS APPLY TO any staff member on the study team for a WFBCCC Institutional Interventional trial. Ultimately, the protocol PI has the primary responsibility for AE identification, documentation, grading and assignment of attribution to the investigational agent/intervention. However, when an AE event as described above is observed, it is the responsibility of the person who observed the event to be sure that it is reported to the DSMC.

What is considered during protocol intervention?

During protocol intervention is considered to be the time period while a patient is on study treatment or during the time period within 30 days of last study treatment (even if patient begins a new (non-study) treatment during the 30 days). This window of 30 days should be the standard window to be used in all protocols unless a specific scientific rationale is presented to suggest that a shorter window can be used to identify events. If it is a trial sponsored by Industry and the sponsor requires a longer window for monitoring of SAEs, then the longer window of time specified by the sponsor should be followed.

What is considered as an Unexpected Grade 4 event?

Any grade 4 event that was not specifically listed as an expected adverse event in the protocol should be considered as unexpected. A grade 4 adverse event can be considered to be unexpected if it is an event that would not be expected based on the treatment being received or if it is unexpected based on the health of the patient. In either case, if there is any uncertainty about whether a grade 4 adverse event is expected or unexpected it should be reported to DSMC.

DSMC notification responsibilities of the person (e.g., nurse) handling the reporting/documenting of the SAE in WISER:

1. Make a phone call (or speak in person) to the appropriate clinical member of the DSMC according to the schedule as listed below (page if necessary).
2. Enter a new SAE into the SAE module that is located in the Subject>> CRA Console in WISER **WITHIN 24 HOURS** of first knowledge of the event. Information can be entered and saved, but the DSMC members will not be notified until a date is entered into the DSMC Notification Date Field. This will ensure that all persons that need to be made aware of the event (i.e., PI, study team members and DSMC members) will be notified; remember to file a copy of the confirmation.
3. Document that the appropriate person(s) on the DSMC has been contacted. Indicate the name of the DSMC clinician that was contacted and the date and time contacted in the Event Narrative field in the SAE console of the particular subject.
4. Document whether or not the protocol should be suspended based on the discussion with the DSMC clinician. This is the major function of the email notification. Enter whether the protocol should be suspended in the Event Narrative Field.
5. Follow up/update the clinical member(s) of DSMC regarding any new developments or information obtained during the course of the SAE investigation and reporting process.

Elements needed to complete the SAE form in the Subject Console in WISER (see Screen Shot 3):

1. Event Date
2. Reported Date
3. Reported by
4. If Grade 5, enter Death Date
5. If Grade 5, enter Death occurred: within 30 days
6. Event Narrative: Brief description (include brief clinical history relevant to this event, including therapies believed related to event). Begin narrative with the DSMC clinician who was notified and Date/Time notified. In addition, state attribution by DSMC clinician as either "Unrelated", "Unlikely", "Possibly", "Probably", or "Definitely". Always include the following here:
 - i. DSMC clinician name, date/time contacted and comments
 - ii. Date of last dose before the event
 - iii. Is suspension of the protocol needed? Y/N
7. Treating Physician comments
8. PI comments, if available
9. Protocol Attribution after discussion with DSMC clinician
10. Outcome (Fatal/Died, Intervention for AE Continues, Migrated AE, Not Recovered/Not Resolved, Recovered/Resolved with Sequelae, Recovered/Resolved without Sequelae, Recovering and Resolving)
11. Consent form Change Required? Y/N
12. SAE Classification ***This is required in order for the email notification to be sent***

table above on the particular day the SAE is being reported. Allow up to 30 minutes for the new DSMC clinician to respond to a phone call or page before contacting the next member in the table. These times (30 minutes) are a general guideline. Best judgment as a clinical research professional should be used giving considerations of the time of day, severity of the SAE, and other circumstances as to when it is appropriate to contact backup clinicians. If the event occurs near the end of day, then leave messages (voice or email) as appropriate and proceed with submitting the DSMC notification form. It is important to take reasonable steps and to document that some type of contact has been initiated to one or more of the clinical members of DSMC.

DSMC CLINICAN RESPONSIBILITY:

It is the responsibility of the DSMC clinician to review all reported events, evaluate the events as they are reported; and communicate a response to the Investigator, event reporter and the members of DSMC. The review will include but not be limited to the information reported; there may be times when additional information is needed in order for an assessment to be made and further communication directly with the investigator may be warranted. DSMC reserves the right to disagree with the Investigator's assessment. If DSMC does not agree with the Investigator, DSMC reserves the right to suspend the trial pending further investigation. If there is any immediate danger or harm that could be present for a future patient based on the information provided in the DSMC report then an immediate suspension of enrollment should be considered.

AMENDMENTS TO PREVIOUS REPORTS

If all pertinent information is unavailable with the initial submission, once the additional information is available **do not submit a new report**. Rather, go to the original email that was sent to the DSMC and using that email "reply to all". Entitle this new email "**Amendment for (list date of event and patient ID)**" this will avoid duplications of the same event. List the additional information being reported. This information needs to be entered into WISER as well. To do this, go to the Subject console and click SAEs on the left column. Click on the appropriate SAE number that needs updating. Then click Update. This will allow additional information to be added.

Acronyms

AE – Adverse Event

DSMC-Data and Safety Monitoring Committee

SAE-Serious Adverse Event

WFBCCC – Wake Forest Baptist Comprehensive Cancer Center

NCI-National Cancer Institute

WISER –Wake Integrated Solution for Enterprise Research

A Randomized Clinical Trial of Prophylactic Risedronate for Patients with Peripheral Lung Tumors Treated with SBRT
Wake Forest Baptist Comprehensive Cancer Center
WFBCCC 99518

Screen Shots:

The following screen shots come from the SAE Console within the Subject Console in WISER.

Screen Shot 1:

